#### 11.3 Sample Size/Accrual Rate

We anticipate enrolling 1 patient every 1-2 two months for approximately 6-12 patients per year. We would like to enroll a total of 30 evaluable patients on trial for robust statistical analysis and to allow for a 20% drop out rate. Enrollment would occur over a three-year period to achieve the enrollment goals.

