### **10.3 Reporting and Exclusions**

#### Evaluation of Toxicity

All patients will be evaluable for toxicity from the time of their first treatment with 5-FU/capecitabine and IFN alpha-2b. Adverse events that occur during screening will not be captured. Adverse events will only be captured until 30 days after the last dose of any investigational drug.

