### **11.2 Statistical Design**

This is a single arm, Phase II trial using a Simon's two-stage design to evaluate the RECIST response rate to 5-FU/capecitabine and interferon alpha-2b in patients with

unresectable or metastatic squamous cell carcinoma of the skin after 3 cycles of treatment. Patients must have received at least one cycle of 5-FU/capecitabine and PEG-IFN

alpha in order to be evaluable for response. We wish to distinguish between a response rate of 10%, which would be uninteresting, and a response rate of >30%, which would merit further testing. Choosing an alpha type error probability of 0.1 and a beta type error probability of 0.1 would mean that in order to proceed beyond the first stage, at least 2 of first 16 patients would have to have responses, and at least 5 of

25 patients (statistics based on 25 evaluateable patients with a total enrollment of 30 patients) would have to respond in order declare this a regimen of interest.

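### Section 11.3 plans 30 evaluable patients, Section 11.2 plans 25 evaluable out of 30 enrolled, and the 5-of-25 rule has no provision for any other number

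*Combined protocol and SAP*

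**What the plan says.** Section 11.2 (Statistical Design) describes a Simon two-stage test of a 10% against a 30% response rate, with these elements:

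- Error rates: "Choosing an alpha type error probability of 0.1 and a beta type error probability of 0.1".
- Stage 1: "at least 2 of first 16 patients would have to have responses".
- Final stage: at least 5 responders of 25, with the note "statistics based on 25 evaluateable patients with a total enrollment of 30 patients".
- Evaluability for response: "Patients must have received at least one cycle of 5-FU/capecitabine and PEG-IFN" alpha.

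Section 11.3 (Sample Size/Accrual Rate) gives the target differently: to "enroll a total of 30 evaluable patients on trial for robust statistical analysis and to allow for a 20% drop out rate". It projects "approximately 6-12 patients per year" and adds "Enrollment would occur over a three-year period to achieve the enrollment goals".

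Section 10.3 has a separate, wider population: "All patients will be evaluable for toxicity from the time of their first treatment". It concerns safety reporting and does not define the denominator of the response test.

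**The concern.** The number 30 is the enrolled total in 11.2 and the evaluable total in 11.3. The two agree only if nobody is lost, yet the same sentence of 11.3 provides for 20% loss.

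The second difficulty remains after that word is corrected. A patient becomes evaluable by receiving one cycle of treatment, so the number evaluable among 30 enrolled is not under the sponsor's control and can fall on either side of 25. Section 11.2 says that the stage 1 decision uses the first 16 patients. It does not say that the final decision uses the first 25, and it gives no rule for fewer or more than 25.

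This is the trial's primary go/no-go test, in an open single-arm study. Without a written rule, the set of patients counted or the cutoff could be settled after responses are known. The error rates depend on both.

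**Working it through.** **Inputs.** From 11.2: null rate 0.10, target rate 0.30, alpha 0.10, beta 0.10, at least 2 of 16 to continue, at least 5 of 25 to succeed, 30 enrolled. From 11.3: 20% drop-out, 6 to 12 patients a year for three years. Assumed here: drop-out means not evaluable for response, and losses are independent between patients.

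**Formula.** With n evaluable patients, final cutoff r and response rate p,

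P(success) = sum over x from 2 to 16 of Bin(x; 16, p) x P(Bin(n - 16, p) >= r - x).

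Setting p = 0.10 gives alpha and p = 0.30 gives power.

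**The plan's own design.** At n = 25 and r = 5, alpha is 0.0951 and power 0.9030. A search over two-stage designs meeting both limits returns this one as the minimax design. Section 11.2 is therefore correct at exactly 25 evaluable.

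**Other evaluable numbers, stage 1 unchanged.**

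| Evaluable | Alpha, cutoff 5 | Power, cutoff 5 | Alpha, cutoff 4 |
|---|---|---|---|
| 22 | 0.062 | 0.834 | 0.167 |
| 23 | 0.072 | 0.861 | 0.184 |
| 24 | 0.083 | 0.884 | 0.201 |
| 25 | 0.095 | 0.903 | 0.217 |
| 26 | 0.107 | 0.918 | 0.234 |
| 30 | 0.159 | 0.954 | 0.292 |

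Below 25, a cutoff of 5 keeps alpha but loses power. Lowering the cutoff to 4 to compensate breaks alpha, which does not fall below 0.10 until 18 evaluable (0.098). Above 25, counting everyone against a cutoff of 5 breaks alpha.

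**From enrolled to evaluable.** 25 x 1.2 = 30, which is evidently how 30 was obtained. But 30 x 0.8 = 24, and 1 - 25/30 = 16.7%. So 30 enrolled allows for about 17% loss. A full 20% needs 25/0.8 = 31.25, or 32.

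**How often 25 is reached.** Let M be the number evaluable, Bin(30, 0.8). Then P(M < 25) = 0.57, P(M = 25) = 0.17 and P(M > 25) = 0.26. All 30 are evaluable with probability 0.8^30 = 0.001.

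**Error rates averaged over M, 30 enrolled, cutoff 5.**

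| Loss | Alpha, first 25 evaluable | Power, first 25 evaluable | Alpha, all evaluable counted |
|---|---|---|---|
| 10% | 0.094 | 0.901 | 0.120 |
| 15% | 0.089 | 0.891 | 0.102 |
| 16.7% | 0.086 | 0.885 | 0.096 |
| 20% | 0.079 | 0.868 | 0.085 |
| 25% | 0.067 | 0.832 | 0.069 |

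**Enrolling until 25 are evaluable.** At 20% loss this takes 31.25 patients on average. The upper accrual projection is 3 x 12 = 36, and P(Bin(36, 0.8) >= 25) = 0.96.

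**The case against.** The strongest reply is that this is one misplaced word. Section 11.2 states the design explicitly, and a 30 that allows for drop-out can only be an enrolled number. That is very probably what was meant, and the 16/25 design is unaffected. But the current text still conflicts, and the corrected word would leave 20% in 11.3 against 16.7% in 11.2.

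A second reply is that 11.2 fixes the denominator at 25, so the inflated alphas belong to a reading the plan does not direct. This largely stands. The figures above 25 are hypothetical, and at 20% loss average alpha stays below 0.10 even on that reading. The cutoff of 4 is likewise not in the plan; it shows only why the cutoff should be fixed in advance.

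A third reply is that drop-out is not the same as non-evaluability. A patient is evaluable after one 21-day cycle, while treatment may run to nine, so late drop-outs still count. If only 10% were non-evaluable, average power would be 0.901 and there would be no shortfall. That dependence is real and should be stated. However, the plan itself uses the drop-out allowance to pass from 25 evaluable to 30 enrolled, so it is fair to judge the plan at that rate.

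Finally, power of 0.87 to 0.885 instead of 0.90 is a modest loss in a phase II trial. This bears on how serious the matter is, and does not remove the inconsistency.

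**Conclusion.** The point holds, and should be fixed. The two sections give incompatible evaluable numbers, and the visible text has no rule for an evaluable number other than 25. The two-stage design itself is correct.

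The likelier consequence at the plan's own 20% loss is a shortfall: power of 0.884 if exactly 24 are evaluable and about 0.87 on average, against 0.90. This rests on two assumptions: that drop-out means non-evaluable for response, and that losses are independent. The excess-alpha case (0.107 at 26, 0.159 at 30) is less likely and arises only if every evaluable patient is counted against an unchanged cutoff.

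**What to change.** - **Section 11.3:** replace 30 evaluable patients with 25 evaluable patients from up to 30 enrolled.
- **Section 11.2, test set:** state that the final decision uses the first 25 evaluable patients in order of enrollment, with any later ones reported descriptively.
- **Section 11.2, shortfall:** state that if fewer than 25 are evaluable the cutoff stays at 5. Alpha then remains below 0.095.
- **Loss and power:** either restate the allowance as 5 of 30 (about 17%, average power about 0.885), or keep 20% and state average power of about 0.87.

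This costs three or four sentences and no additional patients. The price is a stated average power slightly below 0.90. If 0.90 must be kept, the alternative is to enroll until 25 are evaluable. That gives power 0.903 and, at 20% loss, costs one or two more patients on average. A ceiling of 36, the top of the accrual projection in 11.3, would suffice with probability 0.96.

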#### 11.4 Analysis of Secondary Endpoints

Overall survival (OS) (the time from registration to death or date of last contact) and progression free survival (PFS) (patients alive without RECIST progression) are secondary objectives of the study. Kaplan-Meier estimates of overall and progression-free survival rates will be calculated, along with their corresponding 95% confidence intervals. The median, 6-month and 12-month overall and progression free survival rates will be estimated. Adverse events will be collected according the study calendar and tabulated for cumulative evaluation.

[REDACTED]

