## 9. MEASUREMENT OF EFFECT

### Antitumor Effect – Solid Tumors

For the purposes of this study, patients should be re-evaluated for response every nine weeks.

If treatment is held for adverse event recovery thereby extending cycle length, then imaging and tumor measurement intervals may be correspondingly altered so that the patient is imaged every third cycle.

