##### **9.4.2 Duration of overall response**

The duration of overall response is measured from the time measurement criteria are met for CR or PR (whichever is first recorded) until the first date that recurrent or progressive disease is objectively documented (taking as reference for progressive disease the smallest measurements recorded since the treatment started).

The duration of overall CR is measured from the time measurement criteria are first met for CR until the first date that recurrent disease is objectively documented.

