#### **9.5 Progression-Free Survival**

Progression-free survival (PFS) is defined as the duration of time from start of treatment to time of progression or death, whichever occurs first.

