#### 11.1.2 Secondary Objective

To establish the progression free survival (PFS), overall survival (OS), and safety profile (AEs) of the combination of IFN alpha-2b and 5-FU/capecitabine in this patient population at 6 months and 1 year.

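### The 6-month PFS rate is read about 6 days before the third nine-weekly tumour assessment, which biases it upward

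*Combined protocol and SAP*

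**What the plan says.** The secondary objective in Section 11.1.2 covers PFS, OS and safety "in this patient population at 6 months and 1 year". Section 11.4 gives the method: "Kaplan-Meier estimates of overall and progression-free survival rates will be calculated, along with their corresponding 95% confidence intervals". It adds that "The median, 6-month and 12-month overall and progression free survival rates will be estimated". Section 9.5 sets the time origin and the event: "Progression-free survival (PFS) is defined as the duration of time from start of treatment to time of progression or death, whichever occurs first".

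The assessment schedule is in the opening paragraph of Section 9: "For the purposes of this study, patients should be re-evaluated for response every nine weeks". If treatment is held, "imaging and tumor measurement intervals may be correspondingly altered so that the patient is imaged every third cycle".

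No section says which date a PFS progression takes. The nearest rule is in Section 9.4.2, for duration of response, which runs "until the first date that recurrent or progressive disease is objectively documented". The plan gives no scan window, no landmark tied to an assessment and no method for interval-censored data.

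**The concern.** Progression found on a periodic scan is normally recorded at the scan date, although it arose at some time since the previous scan. A Kaplan-Meier rate read just before a scheduled scan therefore misses most of the progressions from the preceding interval. Here that interval is almost complete: about 8 of its 9 weeks lie before the 6-month landmark.

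The reported figure would then be close to an 18-week (about 4-month) PFS rate labelled as a 6-month rate. The shift is always in the regimen's favour. The trial has a single arm, so no control group on the same scan schedule cancels it, and a reader who sets the figure beside 6-month rates from elsewhere could be misled.

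**Working it through.** **Inputs from the documents.** Assessments every 9 weeks (Section 9); PFS counted from start of treatment (Section 9.5); Kaplan-Meier rate at 6 months (Section 11.4). The plan states no expected PFS, so there is no PFS figure of its own to reproduce.

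**Assumptions.** PFS is exponential with a median of 4, 6 or 9 months. Scans fall exactly on schedule. Progression takes the date of the assessment that documents it. A share *f* of events (deaths, or progressions picked up between scans) is dated exactly, whatever its timing.

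**Step 1: timing.** 6 months = 365.25/2 = 182.6 days = 26.1 weeks. Third assessment = 27 × 7 = day 189. Gap = 189 − 182.6 = 6.4 days. Counting 6 months as anything from 180 to 184 days leaves a gap of 9 to 5 days, so the choice of convention does not remove it.

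**Step 2: size.** With S(t) = 0.5^(t/median), t and median in weeks (4, 6 and 9 months = 17.39, 26.09 and 39.13 weeks):

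- True 6-month rate = S(26.1).
- Rate reported if only scans detect events = S(18), because week 18 is the last scan before the landmark.
- Excess with share *f* dated exactly = (1 − *f*) × [S(18) − S(26.1)].

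| Median PFS (assumed) | True S(26.1) | Reported S(18) | Excess, *f* = 0 | Excess, *f* = 0.2 | Excess, *f* = 0.5 |
|---|---|---|---|---|---|
| 4 months | 35.4% | 48.8% | 13.4 points | 10.8 | 6.7 |
| 6 months | 50.0% | 62.0% | 12.0 points | 9.6 | 6.0 |
| 9 months | 63.0% | 72.7% | 9.7 points | 7.8 | 4.9 |

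**Step 3: later landmark.** Read at week 28, the scan-only estimate is S(27) = 34.1%, 48.8% and 62.0%. The true week-28 values S(28) are 32.8%, 47.5% and 60.9%. The excess falls to about 1 point in each case. S(27) is also within about 1 point of the true 6-month rate.

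**Step 4: treatment holds.** At 6 months the scan-only estimate depends on the last scan before the landmark, not on the first one after it. If 3 weeks of holds move the second scan to week 21, the reported rate is S(21) = 43.3%, 57.2% and 68.9%, and the excess is 7.9, 7.2 and 5.9 points, less than in Step 2. Cumulative holds of more than about 26.1 − 18 = 8 weeks would be needed to push the second scan past the landmark.

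**Step 5: precision.** With 25 to 30 patients and a rate of 50%, the 95% half-width is 1.96 × √(0.25/n) = 19.6 to 17.9 points.

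**The case against.** The best defence is that scans are not the only way to find progression. Section 9.2 allows superficial lesions to be measured clinically, the displayed cycles in Section 8 include a physical examination every three weeks, and Section 9.4.1 calls for a repeat assessment 4 weeks after a first response, so a response first seen at week 18 is reassessed at about week 22. In a skin cancer these routes matter. This stands, and it makes the scan-only figures an upper bound. It does not remove the bias: confirmation applies to responders only, the displayed calendar marks tumour measurements only before the study, and Section 9.2 prefers imaging to clinical examination where both are used.

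It is also fair that the date rule for PFS is an assumption, that 6-month PFS is descriptive with no test or threshold attached, that Section 1.2 names only one year, and that the confidence interval is wider than the bias. That interval, however, reflects random error only and neither shows nor corrects a shift in one direction.

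Early scans would help, but modestly: if third scans were spread uniformly within 7 days either side of day 189, about 4% would fall on or before the landmark; within 14 days, about 27%.

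A reader might infer two stronger points that the documents do not support. One is that letting scans move after holds makes the 6-month bias worse. Delaying the third scan, already past the landmark, changes nothing at 6 months, and delaying the second moves it closer and reduces the bias (Step 4). The other is that scans should therefore be fixed to calendar weeks. That would conflict with the primary endpoint, response after 3 cycles (Sections 11.1.1 and 11.2): a patient held for 3 weeks early on would be scanned at week 9 after two cycles.

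**Conclusion.** The concern holds for 6-month PFS. The timing follows directly from the documents. The upward direction follows once progression is dated at documentation, a reasonable reading that the plan does not state for PFS. The size rests on exponential PFS with medians of 4 to 9 months: at most about 10 to 13 points with scan-only detection, and about 5 to 7 points if half of events are dated exactly. The documents give neither the median nor that share.

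This is a predictable, one-directional error in a secondary estimate, and it is worth a small change. It does not touch 6-month OS or the decision on response rate.

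**What to change.** In Sections 11.1.2 and 11.4, replace the 6-month PFS rate with PFS at the third assessment, for example at week 28, just after the week-27 scan. Keep 6-month OS. State that a PFS progression takes the date on which it is documented. For patients whose scans move after holds, and whose third scan may then fall after week 28, add an interval-censored PFS estimate based on actual assessment dates. Leave the Section 9 imaging rule as it is.

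The cost is wording and one extra analysis, with no added scans. The reported rate will be somewhat less favourable and will not sit at a round 6 months.
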